2 LAY SUMMARY

Bleeding affects up to 40% of all trauma patients, up to 30% of all surgery patients and is one of the commonest causes of death for women giving birth. The presentation and features of bleeding are

different between patients – in some cases bleeding is very obvious to recognise, but in other cases bleeding is more “hidden”, for example in the stomach. Bleeding must be stopped promptly to prevent severe illness or death.

Many studies have shown differences in how patients who bleed are treated. There is also variation in how individual patients respond to the same treatment, with some patients doing better than others. Understanding how variation in practice and patient characteristics affect outcomes will help us design and test improvements in care.

Patients in hospital have regular tests that measure levels of the different types of cells in their blood and its ability to clot. For example, a drop in red blood cells can indicate that patients have suffered bleeding. More advanced blood tests are available that can provide more detailed information on why patients are bleeding and what treatments might be most effective.

This study aims to develop a real-time, hospital-wide digital system to identify patients in hospital who have suffered from bleeding and test whether this system could be used in the future to potentially identify patients to recruit into trials of new treatments or blood tests.

To do this, we will:

- Assemble a panel of experts to identify criteria (for example, specific blood test results and drug prescriptions) that could indicate a patient has suffered from bleeding
- Use historical electronic patient records to test how well these criteria identify patients who have received treatments for bleeding (blood transfusion)
- Develop and refine a web-based digital system where the most useful criteria can be applied in “real-time” to identify bleeding patients
- Test how well the digital platform identifies bleeding patients
- Test whether a significant number of patients identified by the digital platform are willing to allow their routine blood samples tested for blood clotting and endothelial factors.

3 SYNOPSIS

Study Title	RE-BLEED: A digital platform for identifying bleeding patients: a feasibility study
Internal ref. no. / short title	RE-BLEED
Study registration	The study will be registered on clinicaltrials.gov
Sponsor	University of Oxford
Funder	Oxford BRC
Study Design	Study incorporating database analysis, cohort observation and laboratory study
Study Participants	Patients with actual or suspected acquired bleeding
Sample Size	
Retrospective data Up to 1,750,000 patient admissions (up to 10 years of admissions)
 
Prospective data Up to 87, 500 will be screened by the digital platform to identify those who may have bled during the six-month recruitment period. Research nurses will review

	electronic records of patients with potential bleeding (identified by the digital platform), with the aim of gaining consent from at least 50 in the last three months of the study.		
Planned Study Period	1/10/2021 to 31/8/2023		
Planned Recruitment period	Retrospective data from the period: 1/3/2011 to 31/8/2022 Prospective study: 1/10/2021 to 31/8/2023		
	Objectives	Outcome Measures	Timepoint(s)
Primary	To test whether a digital platform can efficiently identify patients who have suffered a bleeding event and are willing to consent for the routine blood samples to be used in research.	At least 200 patients correctly identified as having suffered bleeding, of which 40 (20%) provide consent	End of study
Secondary	
 1. To conduct a Delphi process with an expert panel to identify criteria that could be applied in the electronic patient record to identify patients with acquired bleeding 2. To use 10 years' of retrospective data to map bleeding criteria to appropriate data fields within the electronic patient record data sources 3. To encode bleeding criteria into a real-time "algorithm" and display results within a digital web-based platform 4. To measure and refine the accuracy of the algorithm, by 	
 1. List of bleeding criteria 2. Bleeding criteria mapped to appropriate data fields on the electronic patient record 3. Digital platform capable of identifying bleeding patients in real-time 4. Algorithm accuracy before/after refinement 5. List of unique challenges faced by the laboratory team during blood sample retention and analysis 6. Numbers of samples retained and additional blood clotting and endothelial factor results captured from the retained samples. 	End of study

	
manual review of free-text notes of patients identified as bleeding
 
5. Assess the feasibility of sample sequestering by the lab
 
6. Assess the feasibility of performing blood clotting and endothelial factor analysis on the sequestered samples.
		
Intervention(s)	
Non-interventional study
 
 No change to the normal clinical care or treatment of participants. 		
Comparator	None (n/a)		

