Understanding variation in patients’ response to treatments for bleeding requires large studies. This study aims to develop a real-time digital platform, whereby bleeding patients among the whole hospital population can be efficiently identified by an algorithm and approached for their consent to participate in research studies. The platform will also integrate multiple sources of patient data, from which study data sets can be automatically created. In this feasibility study, we will assess the accuracy of the algorithm for identifying bleeding patients and whether a significant proportion (25%) of these patients are willing to consent for their data and routine blood samples to be used for research. Once developed, the digital platform could be deployed across multiple sites to facilitate efficient identification of potential participants for future clinical trials.

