6 OBJECTIVES AND OUTCOME MEASURES

Objectives	Outcome Measures	Timepoint(s) of evaluation of this outcome measure (if applicable)
Primary		
To test whether a digital platform can efficiently identify patients who have suffered a bleeding event and	At least 200 patients correctly identified as having suffered bleeding, of which 40 (20%) provide consent	End of study

are willing to consent for the routine blood samples to be used in research.
		

Secondary
		

 1. To conduct a Delphi process with an expert panel to identify criteria that could be applied in the electronic patient record to identify patients with acquired bleeding 2. To use 10 years’ of retrospective data to map bleeding criteria to appropriate data fields within the electronic patient record data sources 3. To encode bleeding criteria into a real-time “algorithm” and display results within a digital web-based platform 4. To measure and refine the accuracy of the algorithm, by manual review of free-text notes of patients identified as bleeding 5. Assess the feasibility of sample sequestering by the lab 6. Assess the feasibility of performing blood clotting and endothelial factor analysis on the sequestered samples. 	
 1. List of bleeding criteria 2. Bleeding criteria mapped to appropriate data fields on the electronic patient record 3. Digital platform capable of identifying bleeding patients in real-time 4. Algorithm accuracy before/after refinement 5. List of unique challenges faced by the laboratory team during blood sample retention and analysis 6. Numbers of samples retained and additional blood clotting and endothelial factor results captured from the retained samples. 	
End of study

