11 STATISTICS AND ANALYSIS

The statistical aspects of the study are summarised below. A statistical analysis plan (SAP) that will be available from the time that the last participant is recruited. The SAP will be finalised before any analysis takes place.

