11.2.2 Prospective data

Up to 87,500 records will be screened by the digital platform to identify those who may have bled over 2 three-month periods.

In the first three-month period, research nurses will review electronic records of patients with bleeding (identified by the algorithm), we estimate around 250 will experience a bleeding event. Assuming the algorithm has a sensitivity of 80%, we plan to review 200 electronic records.

In the second three-month prospective period, research nurses will approach patients for consent. Based on the assumption that 200 patients will also be identified by the algorithm in this period, we will aim for at least 40 (20%) of patients to consent to their participation.

We will assess the efficacy of the sample retention process being used by the study. This will include the number of samples successfully retained, the number of additional clotting laboratory resulted gained from these samples and any feedback from the laboratory staff regarding challenges they faced.

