11.4 Decision points

There are no decision points in this feasibility study.

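### The protocol sets two consent targets for the same phase: 40 of 200 (20%) as the primary outcome, but 50 in the synopsis sample size and 25% in the Aim

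*Protocol*

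**What the plan says.** The consent target for the final three-month phase appears in five places in the current protocol text.

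- **Section 3 (Synopsis, Primary) and section 6 (Primary):** the outcome measure, worded identically in both, is "At least 200 patients correctly identified as having suffered bleeding, of which 40 (20%) provide consent".
- **Section 11.2.2:** for the second three-month period, "we will aim for at least 40 (20%) of patients to consent to their participation". The base is given just before: "Based on the assumption that 200 patients will also be identified by the algorithm in this period".
- **Section 3 (Synopsis, Sample Size):** nurses review the records of patients flagged by the platform "with the aim of gaining consent from at least 50 in the last three months of the study". No percentage or numerical denominator is attached.
- **Section 5 (Aim):** the study will assess "whether a significant proportion (25%) of these patients are willing to consent for their data and routine blood samples". No count is attached.

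Two further statements bear on how these are read. Section 11.4 says "There are no decision points in this feasibility study". Section 11 introduces "A statistical analysis plan (SAP) that will be available from the time that the last participant is recruited" and adds that it will be finalised before any analysis.

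**The concern.** Consent is half of the primary objective of this feasibility study; the other half is identifying the bleeding patients. The synopsis alone gives both 40 and 50, a few rows apart, and the Aim gives a percentage that matches 50 rather than 40. Sections 7 and 9.2 place consent in the final three months, so these are not targets for different stages. No text presents 50 or 25% as a stretch goal or as an allowance for withdrawals, and the amendment history records no change of target.

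At stake is how the result is judged. With 40 to 49 consents out of 200, one reader could report the primary outcome as met, and another could report that the study missed its stated aim. Both could cite the protocol.

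The denominator adds a second ambiguity. Sections 3 and 6 count patients correctly identified, while section 11.2.2 counts patients the algorithm identifies. Section 9.1 expects some flagged patients not to have bled, so the two groups need not be the same size. The primary outcome also sets 200 as a minimum, which means its own count and percentage agree only if exactly 200 are identified.

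**Working it through.** **Inputs from the protocol (section 11.2.2 unless stated)**
- Expected bleeding events in a three-month period: 250 ("we estimate around 250 will experience a bleeding event", given for the first period)
- Assumed sensitivity: 80%
- Patients identified in the second period: 200
- Consent target: 40 (20%)
- Competing figures: 50 (section 3, Sample Size) and 25% (section 5, Aim)

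**Step 1. Reproduce the plan's own figure.**
250 × 0.80 = 200 identified. 200 × 0.20 = 40 consents. The primary target reproduces.

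**Step 2. Place the competing figures on the same denominator.**
50 / 200 = 25%, and 0.25 × 200 = 50. The synopsis row and the Aim therefore agree with each other and both differ from 40 (20%). There are two competing targets, not three.

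**Step 3. Can a different denominator reconcile them?**
50 is 20% of 250, which would take all expected bleeders as the base. Section 11.2.2 does not do this, and the Aim would still not fit, because 0.25 × 250 = 62.5, or 63 patients. No single denominator makes 40, 50, 20% and 25% all describe one threshold.

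**Step 4. How likely is a result on which the two standards disagree?**
Let X be the number of consents, X ~ Binomial(200, p). This assumes exactly 200 patients and independent decisions. The protocol gives no expected consent rate, so the values of p are illustrative.

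P(40 ≤ X ≤ 49) = P(X ≥ 40) − P(X ≥ 50)

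| True rate p | P(X ≥ 40) | P(X ≥ 50) | P(40 ≤ X ≤ 49) |
|---|---|---|---|
| 20% | 0.528 | 0.049 | 0.479 |
| 22.5% | 0.824 | 0.221 | 0.603 |
| 25% | 0.959 | 0.527 | 0.432 |
| 30% | 0.999 | 0.949 | 0.050 |

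The two standards conflict mainly when the true rate lies near the targets themselves. At 30% both would usually be met.

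**Step 5. Count against percentage when more than 200 are identified.**
Take 250 as an illustration (all expected bleeders found, which is above the assumed sensitivity). Then 40 / 250 = 16% and 50 / 250 = 20%, while 20% and 25% would require 50 and 63 consents. The count of 40 would be met at a rate below the stated 20%.

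**The case against.** The strongest reply is that the governing criterion is not in doubt. Only 40 (20%) is labelled as the primary outcome, it appears three times, and section 11.2.2 derives it. The 50 sits in a synopsis row and the 25% in background prose. No test, power calculation or decision rule uses either figure, and section 11.4 rules out decision points. This stands as a limit on severity: no error rate changes, and someone assessing the labelled outcome would use 40. It does not remove the conflict, because the Aim and the primary outcome address the same question with different figures.

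A recruitment aim may also sit above a success threshold without contradicting it, for instance to allow for withdrawal (section 9.7) or for refusal by a patient who regains capacity (section 9.4.4). The protocol never gives that reason, however, and section 11.2.2 also describes 40 as an aim.

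On the denominator, the 200 in section 11.2.2 is expected bleeders times sensitivity, which is an expected number of true positives. The intended base may therefore be the correctly identified patients. That is a fair reading, but the words used would include false positives.

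Two other objections are partly right. The 250-patient case is only an illustration. As for timing, the SAP is to be finalised before any analysis, which limits the risk of choosing a threshold after the fact. Even so, a SAP that becomes available when the last participant is recruited may come after the consent count is known.

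**Conclusion.** The concern holds. Nothing is miscalculated; the fault is an internal inconsistency between 40 (20%) and 50 (25%) for the same consent phase, with a loosely worded denominator on top. If the true consent rate is between 20% and 25%, the chance of a result that meets one standard and misses the other is about 43% to 60% at the three rates tried. That rests on exactly 200 patients, independent decisions and illustrative rates. The inconsistency itself needs none of these assumptions. It should be fixed because it concerns the success threshold for half of the primary question, but it affects neither an error rate nor the data to be collected.

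**What to change.** Before consent counts are known, state one count, one percentage and one denominator, and use them in section 3 (Sample Size and Primary rows), section 5 (Aim), section 6 and section 11.2.2.

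- **Simplest route:** since 40 (20%) is the labelled and derived outcome, change 50 to 40 in the synopsis Sample Size row and 25% to 20% in section 5.
- **If the sponsor intends 50 (25%):** change the primary outcome in sections 3 and 6 and the text of section 11.2.2 instead.
- **In either case:** say whether the denominator is correctly identified patients or all patients the algorithm identifies in the second three-month period, and whether the count or the percentage governs if more than 200 are identified.

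The cost is a wording amendment in a few places, with no additional patients or data.

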4 ABBREVIATIONS

AVPU	Alert, Verbal, Pain, Unconscious (description of consciousness level)
APTT	Activated Partial Thromboplastin Time
BP	Blood Pressure
CAG	Clinical Advisory Group
CCRG	Critical Care Research Group
CDW	Clinical Data Warehouse
CI	Chief Investigator
CIS	Clinical Information System
CRF	Case Report Form
CTRG	Clinical Trials & Research Governance, University of Oxford
ED	Emergency Department
EDTA	Ethylenediamine tetraacetic acid
HER	Electronic Health Records
GCP	Good Clinical Practice
GCS	Glasgow Coma Scale
GP	General Practitioner
HALT-IT	Haemorrhage ALleviation with Tranexamic acid – InTestinal system
HAT	Hospital Acquired Thrombosis
HAVEN	Hospital Alerting Via Electronic Noticeboard
HRA	Health Research Authority
HTA	Human Tissue Authority

ICD	International Classification of Diseases
ICF	Informed Consent Form
ICO	Information Commissioner's Office
ICU	Intensive Care Unit
IR	Interventional Radiology
IVC	Inferior Vena Cava
JLA	James Lind Alliance
MHP	Major Haemorrhage Protocol
MICE	Multiple imputation by chained equations
NHS	National Health Service
NHS API	NHS Application Programming Interface
ONS	Office of National Statistics
OUH	Oxford University Hospitals NHS Trust
PI	Principal Investigator
PIL	Participant/ Patient Information Leaflet
PPI	Patient and Public Involvement
PR	Pulse Rate
PT	Prothrombin Time
R&D	NHS Trust R&D Department
REC	Research Ethics Committee
SAP	Statistical Analysis Plan
SOP	Standard Operating Procedure
TARN	Trauma Audit Research Network
TXA	Tranexamic acid
UKOSS	United Kingdom Obstetric Surveillance Service
VTE	Venous Thromboembolism
WHO	World Health Organisation
WIMM	Weatherall Institute of Molecular Medicine

5 BACKGROUND AND RATIONALE

What is the health care problem?

Bleeding is a common cause of poor health as well as death (1). A recent UK-wide audit showed that acquired bleeding is most commonly seen in patients admitted for trauma, obstetric, surgical, and gastro-intestinal conditions (2). Bleeding affects up to 40% of all trauma patients, up to 30% of all surgery patients and is one of the commonest causes of death for women giving birth (3). However, bleeding is a treatable and preventable cause of death (4). A recognised feature of deaths due to bleeding is that they often occur soon after bleeding begins, or the patient is admitted to hospital. This emphasises the need for timely interventions (5,6).

Research into acquired bleeding has largely been restricted to clinical trials, focussed on single settings or specific groups of patients. For example, the HALT-IT Trial assessed whether treatment with tranexamic acid is safe and reduced mortality in patients with gastrointestinal bleeding (7). These studies tend to include one clearly defined type of patient with major bleeding and address a single research question. This does not permit a broader investigation of variations in treatment and response across different settings and different groups.

Why is research needed?

The James Lind Alliance’s (JLA) research prioritising partnerships on blood transfusion, blood donation and bleeding rated the “management of major bleeding” as a high priority for future research (8). Previous observational studies have revealed considerable variation in treatment and diagnostic testing across different settings and causes of major bleeding. This variation may reflect altered physiological responses to bleeding, which in turn can be impacted by factors such as the patient’s age (9,10). There is also considerable variation in response to specific treatments across the patient population (11). Some of this variation will be easy to explain. For example, a young woman bleeding after giving birth will be treated differently from an older patient bleeding after surgery. However, patients with similar types of bleeding can also receive different treatments. To investigate variations in treatment and individual responses requires a detailed understanding of the patient’s condition, and of the timing and nature of treatments applied. Moreover, it is likely that some of this variation in practice is due to treatment delays and subsequent impact on patient outcomes, alongside inconsistent uptake of research findings (12).

Complications following treatment for major bleeding include thrombotic events (e.g. pulmonary embolism), which can impact on the long-term health of patients. For example, it is well recognised that trauma and pregnancy are pro-thrombotic conditions, but the balance between bleeding and thrombotic risk remains unclear (13). New resuscitation therapies may be defined by different patterns of risk for thrombosis (14). Understanding natural variation in thromboprophylaxis treatment (e.g. anticoagulants) after major bleeding may help us determine the optimal timing of starting or reintroducing them, potentially giving rise to hypotheses to be tested in a clinical trial.

Aim

Understanding variation in patients’ response to treatments for bleeding requires large studies. This study aims to develop a real-time digital platform, whereby bleeding patients among the whole hospital population can be efficiently identified by an algorithm and approached for their consent to participate in research studies. The platform will also integrate multiple sources of patient data, from which study data sets can be automatically created. In this feasibility study, we will assess the accuracy of the algorithm for identifying bleeding patients and whether a significant proportion (25%) of these patients are willing to consent for their data and routine blood samples to be used for research. Once developed, the digital platform could be deployed across multiple sites to facilitate efficient identification of potential participants for future clinical trials.

6 OBJECTIVES AND OUTCOME MEASURES

Objectives	Outcome Measures	Timepoint(s) of evaluation of this outcome measure (if applicable)
Primary		
To test whether a digital platform can efficiently identify patients who have suffered a bleeding event and	At least 200 patients correctly identified as having suffered bleeding, of which 40 (20%) provide consent	End of study

are willing to consent for the routine blood samples to be used in research.
		

Secondary
		

 1. To conduct a Delphi process with an expert panel to identify criteria that could be applied in the electronic patient record to identify patients with acquired bleeding 2. To use 10 years’ of retrospective data to map bleeding criteria to appropriate data fields within the electronic patient record data sources 3. To encode bleeding criteria into a real-time “algorithm” and display results within a digital web-based platform 4. To measure and refine the accuracy of the algorithm, by manual review of free-text notes of patients identified as bleeding 5. Assess the feasibility of sample sequestering by the lab 6. Assess the feasibility of performing blood clotting and endothelial factor analysis on the sequestered samples. 	
 1. List of bleeding criteria 2. Bleeding criteria mapped to appropriate data fields on the electronic patient record 3. Digital platform capable of identifying bleeding patients in real-time 4. Algorithm accuracy before/after refinement 5. List of unique challenges faced by the laboratory team during blood sample retention and analysis 6. Numbers of samples retained and additional blood clotting and endothelial factor results captured from the retained samples. 	
End of study

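### The primary consent target is stated as both 40 patients and 20%; these agree only at exactly 200 identified, and above 200 the protocol does not say which governs

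*Protocol*

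**What the plan says.** The synopsis and section 6 give the same primary outcome measure, assessed at the end of the study: "At least 200 patients correctly identified as having suffered bleeding, of which 40 (20%) provide consent". No upper limit is set on the number identified, and no data-collection period is named.

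Section 11.2.2 shows where the figures come from. For the first three-month period, "we estimate around 250 will experience a bleeding event", and then "Assuming the algorithm has a sensitivity of 80%, we plan to review 200 electronic records". For the second period the target is conditional on a premise: "Based on the assumption that 200 patients will also be identified by the algorithm in this period". The consent target built on that premise is worded as follows: "we will aim for at least 40 (20%) of patients to consent to their participation". The denominator here is patients identified by the algorithm, whereas section 6 uses patients correctly identified.

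The consent target also appears with other values. The sample size row of the synopsis reads "with the aim of gaining consent from at least 50 in the last three months of the study", and the Aim in section 5 asks "whether a significant proportion (25%) of these patients are willing to consent".

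Section 11.1.2 names the exact (Clopper-Pearson) interval for proportions. Section 11.4 states that the study has no decision points.

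**The concern.** A fixed count and a fixed percentage can be one threshold only if the denominator is fixed. Here the denominator may rise above 200 without limit. Each identified patient beyond 200 leaves the count at 40 but raises the number of consents that 20% requires. There is then a band of results that succeeds on one reading and fails on the other.

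This matters because it is the only numerical success threshold among the study's outcome measures. Section 11 makes the statistical analysis plan available from the time the last participant is recruited. By then the study team may already know the number of consents from running the study, so the choice of reading could be made with the result in view. Reconciling 40 (20%) with the 50 and 25% given elsewhere would not remove the problem: 50 and 25% also agree only at 200 (50/200 = 25%).

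**Working it through.** **Inputs.** Floor of 200 identified, and 40 (20%) consenting (synopsis, section 6). About 250 bleeding events and 80% sensitivity (section 11.2.2). The 250 is stated for the first period. Applying it to the second is an assumption, supported by the protocol's expectation that 200 will be identified there too.

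**The plan's own figures reproduce.** 250 × 0.80 = 200, and 0.20 × 200 = 40. The pair is consistent at the planned number.

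**Above 200.** For n identified, the rate requires 0.20 × n consents, rounded up. The count requires 40 throughout. The readings disagree for any number of consents from 40 to one below the rate requirement.

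| Identified (n) | Consents needed for 20% | 40 consents as a rate | Meets count, misses rate |
|---|---|---|---|
| 200 | 40 | 20.0% | none |
| 201 | 41 | 19.9% | 40 |
| 220 | 44 | 18.2% | 40–43 |
| 225 | 45 | 17.8% | 40–44 |
| 250 | 50 | 16.0% | 40–49 |

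For example, 45 consents among 250 is 18.0%: the count is met and the rate is missed. At the top of the band, 49/250 = 19.6%.

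**Is n above 200 reachable?** Yes, if sensitivity exceeds the assumed 80%. At 90% (an illustrative value), 250 × 0.90 = 225. At 100% it is 250, which is the ceiling for correctly identified patients in one period on the protocol's estimate.

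**How likely is a disagreement?** The table gives the exact binomial probability that consents fall in the ambiguous band. The true consent rates are assumptions, not protocol figures.

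| n | True rate 15% | 18% | 20% | 25% |
|---|---|---|---|---|
| 200 | 0 | 0 | 0 | 0 |
| 220 | 8.5% | 25.6% | 24.7% | 2.8% |
| 250 | 33.5% | 59.0% | 42.9% | 2.6% |

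The ambiguity matters most when true consent is near or somewhat below 20%, and hardly at all when it is 25%.

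**If both periods counted.** The criterion names no period. Taking 200 from each gives 400 identified. Then 20% needs 80 consents, and 40 is 10.0%.

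**The case against.** The strongest reply is that there is a natural reading. Section 11.2.2 derives 40 as 20% of an assumed 200, so a reader could take 20% as the target and 40 as its planned value. Requiring both would have the same effect, since the rate is the stricter condition whenever n exceeds 200. Both readings are reasonable, but the protocol states neither, and the primary outcome itself carries no such condition.

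A second reply is that the analysis plan, to be finalised before any analysis, can settle which figure governs. That reduces the concern but does not remove it: the protocol itself fixes this threshold, and the plan may appear only once recruitment has ended.

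Third, both count and proportion can be reported, and section 11.4 excludes decision points. That stands, and it limits the consequence.

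Several stronger readings may tempt a reader, but the documents do not support them:

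- **A conflict below 200.** A high consent rate among fewer than 200 fails the floor outright. The conflict runs one way only, above 200.
- **Far more than 250 correctly identified in one period.** This exceeds the protocol's own estimate of bleeding events. Comparing 200 with total admissions does not help, because it says nothing about how many patients bleed. Broad starting criteria do not help either: section 9.1 has the algorithm refined for specificity, and false positives are not correctly identified patients.
- **Consent limited by nurse capacity, so that better identification must lower the rate.** No cap on consent approaches is given. The limit of up to 200 in section 9.1 concerns the notes review, and section 9.4.3 speaks of a subset without a number or a reason.

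**Conclusion.** The point holds for more than 200 identified patients. The count and the rate are then different thresholds, and the protocol does not say which decides. On its own estimate of about 250 bleeding events per period, the ambiguous band is up to five results wide at 225 identified (40 to 44 consents) and ten wide at 250 (40 to 49, or 16.0% to 19.6%). It would be wider if both periods were pooled, which the wording does not exclude.

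This rests on two conditions: that the estimate of 250 carries over to the consent period, and that sensitivity exceeds 80%. If exactly 200 are identified, there is no conflict. A reader might infer that the study could reach a wrong go/no-go decision. The documents do not support that, since no formal decision depends on the criterion. The harm is a headline feasibility result that could be reported either way.

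**What to change.** In the synopsis, section 6 and section 11.2.2, restate the primary outcome as two parts, judged separately:

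- **(a)** At least 200 patients correctly identified as having bled.
- **(b)** A consent proportion at or above one target, on one named denominator and period, for example correctly identified patients in the final three-month period. Report it with the exact interval already named in section 11.1.2.

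State that the proportion decides (b), and that the count is only the number expected if exactly 200 are identified.

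Settle the target in the same edit: 20% in the primary outcome and section 11.2.2, 25% in section 5, and at least 50 consents in the synopsis sample size row. Align the denominator too, since section 6 and section 11.2.2 describe it differently.

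The cost is wording only, with no new data or method. The downside for the investigators is that success can no longer be claimed on 40 consents alone when more than 200 patients are identified.
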